9.1.1.1 Repetition of Screening Assessments

Repetition of screening assessment(s) that do not meet eligibility criteria is not permitted, with the following exceptions:

- There is clear evidence of a laboratory error (e.g., hemolyzed sample) or equipment malfunction. In this case, collection of a repeat sample for the appropriate laboratory test may be permitted after discussion with the Vertex medical monitor or authorized designee.
- If a convincing alternative etiology is identified for elevated transaminases, exclusionary liver function test (LFT) levels may be retested within 2 weeks of the original Screening Visit date.
- If an adequate slit-lamp examination could not be conducted (Section 12.6.5).

If repeat values are within the eligibility criteria and completed within the screening window or extended screening window (Section 9.1.1.3), the subject is eligible for the study.

9.1.1.2 Rescreening

Rescreening may be considered only with approval of the Vertex medical monitor. The investigator (or an appropriate authorized designee at the study site) will confirm the assessments (e.g., number/type of blood sample assessments) required for rescreening with the Vertex medical monitor. *CFTR* genotyping and sweat chloride testing do not need to be repeated. If a subject has had an OE including an adequate slit-lamp examination within 12 weeks, the OE does not need to be repeated. If a subject is rescreened, the screening window will begin once the first rescreening assessment has been initiated.

9.1.1.3 Extension of Screening Window

A subject may have the screening window extended by 2 weeks for the following reasons upon approval by the Vertex medical monitor:

- Repetition of screening assessments (Section 9.1.1.1)
- Unexpected operational or logistical delays (e.g., delayed drug shipment)
- To meet the eligibility criteria
- Scheduling of the OE (Section 12.6.5)
- Availability of required equipment

The screening window can be extended by 4 weeks if a slit-lamp examination must be repeated (Sections 9.1.1.1 and 12.6.5).

9.1.2 Treatment Period

Treatment Period assessments are listed in Table 3-1, Table 3-2, Table 3-3, and Table 16-1.

In Part A, subjects will be administered 25 mg, 50 mg, or 75 mg q12h, or other appropriate dose of ivacaftor based on emerging PK data (by weight, see Section 9.3.2), on Days 1 through 3, and 1 morning dose on Day 4. Subjects will be outpatients during the study; visits will occur on Day 1, Day 4, and Day 5. Telephone contact will also occur in the evening of Day 1 and the morning of Day 2.

After preliminary analysis of PK and safety data from Part A is performed and dose selection for Part B is confirmed, subjects in Part B Cohorts 5 and 6 will be administered 25-mg, 50-mg, or 75-mg ivacaftor (by weight, see Section 9.3.2) or other appropriate doses (to be determined based on PK data from Part A) administered q12h for 24 weeks. All subjects enrolled in Cohort 7 will receive a 25 mg dose of ivacaftor q12h until the subject reaches the age of 6 months, at which time the ivacaftor dose for each subject will be reassessed and adjusted based on body weight (Section 9.3.2). For subjects who participated in Part A, the starting dose in Part B may be different than that of Part A based on body weight on Day 1. Subjects will be outpatients during the study; visits will occur on Day 1 and Weeks 2, 4, 8, 12, 18, and 24; and a telephone contact will occur on Day 3.

In Part A/B Cohort 8, subjects will be administered an initial low dose of ivacaftor (5.7 mg q12h or 11.4 mg q12h based on their Day 1 age and weight) from Day 1 up to Day 15 (see Section 9.3.2). Subjects will be outpatients during the study; visits will occur on Day 1, Day 4, Day 15, Week 4, Week 8, Week 12, Week 18, and Week 24. On Day 4, PK samples will be collected before the morning dose, between 2 to 4 hours and between 6 to 8 hours after the morning dose. The subject's Day 4 PK data will be used to calculate exposure to determine a dose that is expected to bring the exposure for the subject closest to the adult median. This dose or potential dose adjustment will be communicated in writing to the principal investigator to administer to the subject on Day 15. At the Day 15 Visit, a trough PK sample will be collected before the morning dose. The ivacaftor dose will be adjusted based on the Day 4 PK data if necessary, to either 5.7, 11.4, 17.1, 22.8, or 25 mg, and the adjusted dose will be administered q12h starting with the evening dose on Day 15. The subject is intended to remain on the same dose from Day 15 until the subject is 4 months of age and at least 5 kg at which time the recommended age- and weight-appropriate dose(s) will be administered. At the Week 8 Visit, PK samples will be collected before the morning dose, and between 2 to 4 hours and between 6 to 8 hours after the morning dose. The subject's Week 8 pre- and post-dose PK data will be used to more fully characterize the PK profile. Additional PK samples will be collected before the morning dose on the Week 4, 12, 18, and 24 Visits to characterize the longitudinal PK profile. The entire treatment period of the study will be 24 weeks, after which subjects will be eligible to enroll in an Extension Study.

9.1.3 Follow-up

Follow-up assessments are listed in Part A [Table 3-1](#), Part B [Table 3-3](#), and Part A/B Cohort 8 [Table 16-1](#).

In Part A, there will be a Follow-up Telephone Call (Day 14 ± 2 days) and a Follow-up OE (see Section 9.1.3.1) for all subjects.

In Part B and in Part A/B Cohort 8, there will be a Follow-up Visit 4 weeks ± 7 days after the last dose of study drug.

All subjects who complete 24 weeks of study drug treatment in Part B or Part A/B Cohort 8 will be eligible to enroll in the open-label treatment arm of the Extension Study. The Follow-up Visit will not be required for subjects who enroll in the treatment arm of Extension Study.

Subjects who prematurely discontinue study drug treatment in Part B or in Part A/B Cohort 8, and subjects who complete 24 weeks of study drug treatment in Part B or Part A/B Cohort 8, but

do not enroll in the treatment arm of the Extension Study, will be required to complete the Follow-up Visit. The Follow-up Visit will not be required:

- If the ETT Visit occurs 3 weeks or later after the last dose of study drug.
- In the event that the subject initiates treatment with commercially available ivacaftor within 3 weeks of the final scheduled treatment visit in Part B or Part A/B Cohort 8, or the ETT Visit.

Subjects who prematurely discontinue study drug treatment and subjects who complete 24 weeks of study drug treatment in Part B or Part A/B Cohort 8, but do not enroll in the treatment arm of the Extension Study, will be eligible to enroll in the observational arm of the Extension Study. Subjects who are eligible will enroll in the Extension Study as soon as enrollment is open.

9.1.3.1 Follow-up Ophthalmologic Examination

In Part A, there will be a Follow-up OE 8 weeks \pm 14 days after the last dose of study drug. For subjects who have the Part A Follow-up OE within 6 months of enrolling in Part B, a screening OE for Part B is not required.

In Part B, subjects who prematurely discontinue study drug treatment and received at least 1 dose of ivacaftor treatment in Part B will have a Follow-up OE 24 weeks \pm 14 days after the last dose of study drug. Subjects enrolling into the Extension Study within 24 weeks after the last dose of study drug are not required to have the Part B Follow-up OE (the OE will be performed in the Extension Study instead).

In Part A/B Cohort 8, subjects who prematurely discontinue study drug treatment and received at least 1 dose of ivacaftor treatment in Part A/B Cohort 8 will have a Follow-up OE 12 weeks \pm 14 days after the last dose of study drug. Subjects enrolling into the Extension Study within 12 weeks after the last dose of study drug are not required to have the Part A/B Cohort 8 Follow-up OE (the OE will be performed in the Extension Study instead).

Subjects who initiate treatment with commercially available ivacaftor within 3 weeks of the ETT Visit will not have the Part B or Part A/B Cohort 8 Follow-up OE.

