Subjects who complete 24 weeks of study drug treatment who elect not to enroll in the treatment arm of the Extension Study will be required to complete the Follow-up Visit and will be eligible to enroll in the observational arm of the Extension Study. The Follow-up Visit will not be required in the event that the subject initiates treatment with commercially available ivacaftor within 3 weeks of the Week 24 Visit. Subjects who prematurely discontinue treatment before their last scheduled dose will be required to complete the ETT Visit, Follow-up Visit, and Follow-up OE. The Follow-up Visit will not be required:

- If the ETT Visit occurs 3 weeks or later after the last dose of study drug.
- In the event that the subject initiates treatment with commercially available ivacaftor within 3 weeks of the ETT Visit.

Subjects who prematurely discontinue study drug treatment will be eligible to enroll in the observational arm of the Extension Study. Subjects enrolling into the Extension

Study within 24 weeks after the last dose of study drug are not required to have the Follow-up OE (the OE will be performed in the Extension Study).

Part A/B Cohort 8:

Subjects 1 to <4 months of age, ≥ 38 weeks gestation, and weighing at least 3 kg at the time of treatment initiation (Day 1), will receive an initial low dose of ivacaftor (5.7 mg q12h or 11.4 mg q12h based on their Day 1 age and weight) from Day 1 up to Day 15. Subjects 3 months of age must weigh ≥ 5 kg on Day 1. This initial low dose is based on prior age- and weight-based simulations of exposure which accounts for potential variability in metabolic enzyme maturation affecting exposures. The initial dose is expected to result in exposures within or below the adult exposure range. On Day 4, PK samples from each subject will be collected before and after dosing and analyzed to determine the exposure and assess whether the initial dose needs to be adjusted to better match the median adult exposure.

Part A/B Cohort 8 of this study includes:

- Confirmed genotype; genotype testing is expected to be initiated prior to screening and results must be available prior to Day 1
- Screening Period (Day -28 to Day -14)
 - Due to limitations in the volume of blood that should be collected from the 1- to <4-month-old age group in a 28-day span, screening should be completed at least 14 days prior to Day 1 (treatment initiation)
- Initial Treatment Period (Day 1 up to Day 15):

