- h The screening OE may be performed predose on Day 1. If an adequate slit-lamp examination cannot be conducted at the Part B screening, subjects will not be enrolled in Part B until an adequate repeat slit-lamp examination is completed (within 4 weeks of the Screening Period) and eligibility criteria regarding the ophthalmologic findings are met. If an adequate slit-lamp examination cannot be conducted at any visit where it is required, the subject will continue to receive study drug until an adequate repeat examination is completed (within 4 weeks of the study visit); if an adequate slit-lamp examination cannot be conducted at the second examination or a lens opacity or cataract is identified, study drug dosing will be discontinued. A screening OE will not need to be conducted for subjects who have the Part A Follow-up OE within 6 months of enrolling in Part B.
- i To minimize blood draws, the Screening Visit and Day 1 clinical laboratory assessments will be combined into a single blood draw taken up to 9 days before Day 1 dosing. The results must be received and reviewed before the first dose of study drug. All blood samples will be collected while subjects are in a seated or supine position.
- j PK samples will be collected before the morning dose and between 2 and 4 hours and between 6 and 8 hours after the morning dose on Week 2. PK samples will be collected before the morning dose and 1 hour and 4 hours after the morning dose on Week 8. PK samples will be collected before the morning dose and between 2 and 4 hours after the morning dose on Week 24.
- k PK sample collection is optional at Week 24 for subjects who undergo MBW.
- l At Screening a sweat chloride test must be performed if the sweat chloride value is not available in the subject's medical records and the value is needed to establish eligibility. For subjects with sweat chloride values documented in their medical records and for whom it is not needed to establish eligibility, the sweat chloride test at screening is not required. Subjects who had a sweat chloride test during Screening for Part A will not require repeat testing during Screening for Part B. At the Day 1 Visit, the sweat chloride test must be performed before the morning dose. At the Week 2, 12, and 24 Visits, the sweat chloride test must be performed within a window of ± 2 hours relative to the morning dose of the study drug.

Table 3-2 Study VX15-770-124: Part B (Screening and Treatment Periods)

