^b The Follow-up Visit is not required if the subject completes the Part B treatment period and enrolls in the treatment arm of the Extension Study. For all other subjects, the Follow-up Visit is not required if the ETT Visit occurs 3 weeks or later after the last dose of study drug (ivacaftor) or in the event that the subject initiates treatment with commercially available ivacaftor within 3 weeks of the final scheduled treatment visit or ETT Visit.

^c Subjects who prematurely discontinue ivacaftor treatment in Part B and received at least 1 dose of ivacaftor treatment in Part B will have a Follow-up OE 24 weeks after the last dose of study drug. Subjects enrolling into the Extension Study within 24 weeks after the last dose of study drug are not required to have the Follow-up OE (the OE will be performed in the Extension Study instead).

^d weight must be measured with the subject in a dry diaper or dry underclothes only (see Section 12.5.1 for details).

^e Full physical examinations will be performed at the ETT Visit and Follow-up Visit.

^f Vital signs include blood pressure (systolic and diastolic), temperature, heart rate, respiration rate, and pulse oximetry. The subject should rest for at least 5 minutes, if possible, before having vital signs measured. Temperature must be obtained by the same method throughout the study.

^g The subject should rest for at least 5 minutes, if possible, before having the ECG performed. The ECG will be performed before any other procedures that may affect heart rate, such as blood draws.

^h All blood samples will be collected while subjects are in a seated or supine position.

ⁱ The OE for the ETT Visit will be conducted for all subjects who prematurely discontinue study drug dosing. If the ETT Visit occurs within 12 weeks of the subject's last OE, the OE at the ETT Visit will not be required. In addition, these subjects will be eligible to enroll in an observational arm of the Extension Study for long-term follow-up OE.

Table 3-3 Study VX15-770-124: Part B (Early Termination of Treatment Visit and Follow-up Period)

	Early Termination of Treatment Visit^a	Follow-up Visit^b	Follow-up Ophthalmologic Examination^c
Event/Assessment	As Soon as Possible After the Last Dose of Study Drug	4 Weeks (± 7 Days) After the Last Dose of Study Drug	24 Weeks (± 14 Days) After the Last Dose of Study Drug

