Subjects who complete 24 weeks of study drug treatment who elect not to enroll in the treatment arm of the Extension Study will be required to complete the Follow-up Visit (4 weeks \pm 7 days after the last dose of study drug) and will be eligible to enroll in the observational arm of the Extension Study. The Follow-up Visit will not be required in the event that the subject initiates treatment with commercially available ivacaftor within 3 weeks of the Week 24 Visit.

Subjects who prematurely discontinue study drug treatment before their last scheduled dose will be required to complete the ETT Visit, Follow-up Visit, and Follow-up OE (see Section 9.1.3.1). The Follow-up Visit will not be required:

- If the ETT Visit occurs 3 weeks or later after the last dose of study drug.
- In the event that the subject initiates treatment with commercially available ivacaftor within 3 weeks of the ETT Visit.

Subjects who prematurely discontinue treatment will be eligible to enroll in the observational arm of the Extension Study. Subjects who are eligible will enroll in the Extension Study as soon as enrollment is open.

Figure 9-1 Schematic of Study Design

OE: ophthalmologic examination

^a Part A Follow-up OE will occur approximately 8 weeks after last dose of study drug.

^b All subjects who complete 24 weeks of study drug treatment will be eligible to enroll in the open-label treatment arm of the Extension Study. All other subjects will be eligible to enroll in the observational arm of the Extension Study. Subjects who prematurely discontinue will have the Part B Follow-up OE approximately 24 weeks after last dose of study drug.

Part A/B Cohort 8:

Subjects 1 to <4 months of age, ≥ 38 weeks gestation, and weighing at least 3 kg at the time of treatment initiation (Day 1) will receive an initial low dose of ivacaftor (5.7 mg q12h or 11.4 mg q12h based on their Day 1 age and weight) from Day 1 up to Day 15 (Figure 9-2). Subjects 3 months of age must weigh ≥ 5 kg on Day 1. This initial low dose is based on prior age- and weight-based simulations of exposure which accounts for potential variability in metabolic enzyme maturation affecting exposures. The initial dose is expected to result in exposures within or below the adult exposure range. On Day 4, PK samples from each subject will be collected before and after dosing and analyzed to determine the exposure and assess whether the initial dose needs to be adjusted to better match the median adult exposure.

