Subjects who prematurely discontinue treatment before their last scheduled dose will be required to complete the ETT Visit, Follow-up Visit, and Follow-up OE. The Follow-up visit will not be required:

- o If the ETT Visit occurs 3 weeks or later after the last dose of study drug.
- o In the event that the subject initiates treatment with commercially available ivacaftor within 3 weeks of the ETT Visit.

Subjects who prematurely discontinue study drug treatment will be eligible to enroll in the observational arm of the Extension Study. Subjects who are eligible will enroll in the Extension Study as soon as enrollment is open. Subjects enrolling into the Extension Study within 24 weeks after the last dose of study drug are not required to have the Follow-up OE (the OE will be performed in the Extension Study).

Figure 6-1 Schematic of Study Design

OE: ophthalmologic examination

Part A Follow-up OE will occur approximately 8 weeks after last dose of study drug.

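### In Part B and Cohort 8 the protocol's body text lets an early discontinuer leave with no post-baseline eye examination, and the schedules, synopsis and SAP conflict with that text

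*Protocol*

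**What the plan says.** **Scheduled OEs.** In Part B and Cohort 8 they fall at screening, Week 12 and Week 24. For Part B, Table 3-2 footnote h says "The screening OE may be performed predose on Day 1". Table 3-4 footnote i likewise lets the Cohort 8 screening OE be done at any point before the first dose.

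**ETT OE.** Section 12.6.5, written for both parts, and Table 3-3 footnote i, for Part B, say: "If the ETT Visit occurs within 12 weeks of the subject's last OE, the OE at the ETT Visit will not be required". Neither requires that last OE to have followed a dose.

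**Follow-up OE.** Section 9.1.3.1 says "Subjects who initiate treatment with commercially available ivacaftor within 3 weeks of the ETT Visit will not have the Part B" or Cohort 8 Follow-up OE. For Part B, other places read differently:

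- Synopsis: "Subjects who prematurely discontinue treatment before their last scheduled dose will be required to complete the ETT Visit, Follow-up Visit, and Follow-up OE".
- Figure 9-1 footnote b: "Subjects who prematurely discontinue will have the Part B Follow-up OE approximately 24 weeks after last dose of study drug".
- Table 3-3 footnote c: early discontinuers "will have a Follow-up OE 24 weeks after the last dose of study drug", with an exemption only for Extension Study enrolment. SAP Table 11-3 footnote c matches it.
- Table 3-3 footnote b: the commercial exception, "in the event that the subject initiates treatment with commercially available ivacaftor within 3 weeks of the final scheduled treatment visit or ETT Visit", applies to the Follow-up Visit only.
- SAP 6.1: the only stated exemption is "Subjects enrolling into the Extension Study within 24 weeks after the last dose of study drug are not required to have the Follow-up OE".

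**The concern.** OEs are a named component of the primary safety endpoint in Part B (Section 8.2.1) and Cohort 8 (Section 8.3.1), and SAP 8.4.6 reports the incidence of cataracts or lens opacities. A dosed infant with no slit-lamp examination after the first dose adds nothing to that result, and the cohorts are very small.

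The 12-week skip is sensible when the last OE was on treatment. It is not sensible when the last OE came before the first dose, because such an examination cannot show a treatment-emergent opacity. Normally the Follow-up OE would fill the gap, but the commercial-start waiver removes it. Because the documents disagree, two sites could also handle the same infant differently, each with text to support it.

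**Working it through.** **Step 1. Set the rules side by side.** Section 12.6.5 cites Table 16-1 as the Cohort 8 schedule. Table 16-1 is the mutation list, so Table 3-4 must be meant.

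| Rule | Part B | Cohort 8 |
|---|---|---|
| ETT OE skipped if an OE was done within 12 weeks | Stated in 12.6.5, Table 3-3 footnote i and the SAP copy of that footnote | Stated in 12.6.5; Table 3-4 and its SAP copy mark an OE at ETT with no such skip |
| Follow-up OE waived on a commercial start within 3 weeks of ETT | Stated in 9.1.3.1; absent from Table 3-3 footnote c, the synopsis, Figure 9-1 footnote b, SAP 6.1 and SAP Table 11-3 footnote c | Stated in 9.1.3.1, Table 3-4 footnote c and its SAP copy |

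The gap needs both rules. The body text gives both rules for both parts. In each part, one rule is also in the schedule and the other is not.

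**Step 2. How late can the ETT OE be skipped on the screening OE alone?** Twelve weeks is 84 days, and there is no Day 0. For an OE on Day -k, the latest ETT day is 84 - k + 1; for an OE on Day 1 it is 1 + 84. The latest qualifying commercial start is 21 days after that.

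| Screening OE | Latest ETT day | Latest commercial start |
|---|---|---|
| Day 1, predose | 1 + 84 = 85 | 106 |
| Day -14 | 84 - 14 + 1 = 71 | 92 |
| Day -28 | 84 - 28 + 1 = 57 | 78 |
| Day -42 (2-week extension, Section 9.1.1.3) | 84 - 42 + 1 = 43 | 64 |
| Day -56 (4-week extension) | 84 - 56 + 1 = 29 | 50 |

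The Week 12 OE is due on Day 84 ± 5, so Day 79 to 89. Before it, no post-baseline OE is scheduled.

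**Step 3. What must happen together?** Treatment stops before the Week 12 OE. The ETT Visit falls within 12 weeks of the screening OE. Commercial ivacaftor starts within 3 weeks of ETT. The infant does not join the Extension Study. An unscheduled post-baseline OE would also close the gap.

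**Step 4. Could a Cohort 8 infant get commercial drug in time?** Take a month as 30.44 days and ages as exact on Day 1. The infant reaches label age L on Day 1 + (L - age) × 30.44.

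| Age on Day 1 | 4-month label (Appendix A) | 6-month label (Section 5.3) |
|---|---|---|
| 3 months | Day 31 | Day 92 |
| 2 months | Day 62 | Day 123 |
| 1 month | Day 92 | Day 153 |

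The latest possible commercial start is Day 106. Under a 4-month label all three ages fit, although the 1-month infant needs a screening OE on Day -14 or later (71 + 21 = 92). Under a 6-month label only infants aged about 6 - 105/30.44 = 2.55 months or more fit. The documents give both label ages.

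**Step 5. Size.** One unexamined infant is 1/6 = 16.7% to 1/10 = 10% of Cohort 8, or 1/5 = 20% of a Part B cohort at its planned minimum.

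**The case against.** The strongest reply concerns Cohort 8. A site following Table 3-4 would do the ETT OE, and the gap would close. Part B has the skip in its schedule, but the documents do not show commercial access when Cohorts 5 to 7 were dosed. So neither part has both an undisputed skip and a documented commercial route. This stands as a limit on likelihood. It does not remove the route in the body text, and if Table 3-4 governs, Section 12.6.5 needs correcting.

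Other replies:

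- **The waiver can be found.** Protocol Section 9.1 and Section 12.6.5 both point to Section 9.1.3.1 for the Follow-up OE. True, but Table 3-3 footnote c still states a different rule.
- **The waiver is reasonable.** An examination 12 or 24 weeks after the last study dose, with commercial drug taken meanwhile, is hard to attribute. That supports waiving the Follow-up OE. It does not support using a predose examination in place of the ETT OE.
- **The Extension Study covers this.** Its observational arm is offered for long-term eye follow-up, but enrolment is optional.
- **Some infants cannot skip.** If a Part B infant's qualifying Part A examination is more than 12 weeks old at ETT, the ETT OE is required. Correct, and those infants are outside the concern.
- **It is late.** SAP 9.1 describes the interim analyses in the past tense, with Cohort 8's following completion of study participation. New wording cannot add examinations for infants already treated.

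**Conclusion.** The point holds as a gap in the protocol's body text plus two conflicts between documents: over the Part B Follow-up OE, and over the Cohort 8 ETT OE. An infant who stops early can satisfy Sections 12.6.5 and 9.1.3.1 and have no eye examination after the first dose. The exposed period runs to ETT Day 57 to 85 within the ordinary 28-day screening window, and ends sooner if screening was extended. The conclusion takes the body text as written and assumes no unscheduled OE. Frequency is unknown, since the documents give no rate of early stopping or commercial starts.

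Three stronger readings are not supported.

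- A reader might infer that the SAP would count an unexamined infant as cataract-free. SAP 8.1 treats a visit without a measurement as missing and does not impute. SAP 8.4.6 leaves the percentage base unstated, which is missing detail and not a bias in the plan. SAP 8.4 also lists all safety data by subject.
- A reader might infer that commercial supply was available in the window. Appendix A implies approval from 4 months of age, while Section 5.3 says 6 months. Neither documents actual access.
- A reader might infer that infants did leave unexamined. Nothing in the documents shows this.

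The change is worth making because it protects a primary safety component at little cost. It does not call the safety analysis as a whole into question.

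**What to change.** 1. In Section 12.6.5 and Table 3-3 footnote i, allow the ETT OE to be skipped only if a post-baseline OE was done within 12 weeks. State the same rule in Table 3-4.
2. Keep the commercial-start waiver of the Follow-up OE only for subjects with at least one post-baseline OE. Word it identically in Section 9.1.3.1, Table 3-3 footnote c, Table 3-4 footnote c, the synopsis and the SAP (6.1 and both schedule copies).
3. For subjects already treated, state which rule was applied for the Part B Follow-up OE and the Cohort 8 ETT OE, and report by cohort how many had no post-baseline OE.

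The cost is an occasional dilated slit-lamp examination at an ETT Visit that already takes place, some aligned wording, and one added count in the OE table. No new analysis window is needed: an ETT OE in the exposed period falls within the SAP's Week 12 OE window (Study Days 2 to 126). Items 1 and 2 help only infants still to be treated. Item 3 is the part that can still be done for those already treated.
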